8.7.5 Effectiveness endpoints

To assess the effectiveness of lorlatinib, the following endpoints will be collected via the DCT or derived:

Endpoint	Source Variable (if endpoint derived)	Description/Derivation
Objective tumor response of primary tumor (soft tissue), soft		Collected by the DCT at each visit. Outcomes include complete response (CR), partial response

PFIZER CONFIDENTIAL

tissue metastasis, and bone metastasis		(PR), stable disease (SD) and progressive disease (PD).												
Bone marrow response		Collected by the DCT at each visit. Outcomes include CR, PD, minimal disease (MD) and SD.												
HCP Reported Objective Response		Collected by the DCT at each visit. Outcomes include CR, PR, minor response (MR), SD and PD.												
Derived Objective Response	Objective Tumor response components	
Derived and compared for robustness to the HCP Reported Objective Response applying the following rules:
 
  
 RESPONSE	CRITERIA	
   
 Complete Response (CR)	All components meet criteria for CR	
 
 Partial Response (PR)	PR in at least one component and all other components are either CR, MD (Bone marrow), PR (Soft tissue or Bone) or Not involved (NI); no component with PD.	
 
 Minor Response (MR)	PR or CR in at least one component but at least one other component with SD; no component with PD.	
 
 Stable Disease (SD)	SD in one component with no better than SD or NI in any other component; no component with PD.	
 
 Progressive Disease (PD)	Any component with PD	
  
	RESPONSE	CRITERIA	Complete Response (CR)	All components meet criteria for CR	Partial Response (PR)	PR in at least one component and all other components are either CR, MD (Bone marrow), PR (Soft tissue or Bone) or Not involved (NI); no component with PD.	Minor Response (MR)	PR or CR in at least one component but at least one other component with SD; no component with PD.	Stable Disease (SD)	SD in one component with no better than SD or NI in any other component; no component with PD.	Progressive Disease (PD)	Any component with PD
RESPONSE	CRITERIA													
Complete Response (CR)	All components meet criteria for CR													
Partial Response (PR)	PR in at least one component and all other components are either CR, MD (Bone marrow), PR (Soft tissue or Bone) or Not involved (NI); no component with PD.													
Minor Response (MR)	PR or CR in at least one component but at least one other component with SD; no component with PD.													
Stable Disease (SD)	SD in one component with no better than SD or NI in any other component; no component with PD.													
Progressive Disease (PD)	Any component with PD													
Best Overall response	HCP Reported Response	Derived as the best overall response taking the HCP Reported Response observed up to the data cut-off date for a specific milestone. (The												

PFIZER CONFIDENTIAL

	Repeated using Derived Objective Response	sequence order from best to worst is CR, PR, MR, SD, PD.)
Overall Response Rate (ORR)	Best Overall Response	Derived as Best overall response of CR+PR of the total population observed up to the data cut-off date for a specific milestone.
Duration of response	Treatment Start and HCP Reported Response Date	Derived as (Date of PD or death, whichever occurs first) – (Date of PR or CR, whichever occurs first) + 1
Progression free survival (PFS)	Treatment Start and HCP Reported PD/Death Date	Derived as (Date of PD or death (by any cause in the absence of PD)) – (Treatment start date) + 1
Duration of treatment	Treatment Start and Stop Dates	Derived as (Treatment stop date) – (Treatment start date) + 1
Overall survival (OS)	Treatment Start and Death Dates	Derived as (Date of death) – (Treatment start date) + 1

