8.7.8 Missing data

Statistical summaries, figures and listings will be based on all available data, as observed. Missing data will not be imputed with the exception of partial dates as per below. However, the amount of missing data will be reported.

For the endpoints requiring date derivations such as duration of response, time to event, the following imputation for partial dates will be applied:

- Missing year: no imputation with date remaining as missing
- Missing month: impute as month 6 (June, mid-year approximately)
- Missing day: impute as 15 (mid month approximately)

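### The derived response table gives no category to CR at a soft tissue or bone site with marrow minimal disease, although PR with minimal disease is scored PR

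*Combined protocol and SAP*

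**What the plan says.** Section 8.7.5 collects responses for primary tumor (soft tissue), soft tissue metastasis and bone metastasis as CR, PR, SD or progressive disease (PD). For bone marrow it states: "Outcomes include CR, PD, minimal disease (MD) and SD". Marrow thus has no PR level.

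The derived objective response is then built from these rows:

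- CR: "All components meet criteria for CR".
- PR: "PR in at least one component and all other components are either CR, MD (Bone marrow"; the row goes on to allow PR in soft tissue or bone and NI, with no PD.
- Minor response (MR): "PR or CR in at least one component but at least one other component with SD", with no PD.
- SD: "SD in one component with no better than SD or NI in any other component", with no PD.
- PD: PD in any component.

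There is no residual or unclassifiable row. Best overall response (BOR) is taken from the HCP-reported response and repeated on the derived response, and its "sequence order from best to worst is CR, PR, MR, SD, PD". The overall response rate (ORR) counts a BOR of CR or PR over the total population. Section 8.7.6 uses the derived response as a robustness check on the HCP call.

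**The concern.** The PR row admits marrow MD only as a companion to a component that is itself PR. If the last PR site improves to CR while the marrow stays at MD, the patient leaves the PR row and enters no other. A deeper response therefore removes the category, which cannot be squared with a scale that ranks CR above PR.

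What is at stake is the robustness check. A patient with CR plus MD at some visit, and no visit that the table classifies as CR or PR, stays in the denominator of an ORR computed on the derived response but cannot enter its numerator. If the HCP calls that visit a response, the table itself produces the disagreement. For these patients the error runs one way: a responder can be missed, never added.

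**Working it through.** The plan gives no figure to reproduce, so the check is of the rules themselves.

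**Step 1: one pattern, row by row.** Every component other than the two named is CR or NI.

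| Row | CR at one site, marrow MD, rest CR or NI | PR at one site, marrow MD, rest CR or NI |
|---|---|---|
| CR | fails, marrow is MD | fails |
| PR | fails, no component is PR | met |
| MR | fails, no component is SD | fails |
| SD | fails, no component is SD | fails |
| PD | fails | fails |
| Result | no category | PR |

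Marrow MD with every other component NI fails all five rows in the same way.

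**Step 2: all patterns, four components.** Each of the three sites takes CR, PR, SD, PD or NI (NI comes from the rules); marrow takes CR, MD, SD, PD or NI. Excluding all-NI, there are 5^4 − 1 = 624 patterns, and 4^4 − 1 = 255 have no PD. Use the most generous reading that keeps the rows' wording: NI is ignored in the CR row, and MD counts as no better than SD in the SD row.

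- CR: 2^4 − 1 = 15
- PR: sites from CR, PR, NI with at least one PR, 3^3 − 2^3 = 19; marrow CR, MD or NI, 19 × 3 = 57
- SD: 2^3 × 3 − 2 = 22
- No category: CR with MD, 2^3 − 1 = 7; MD alone, 1; total 8
- MR: 255 − 15 − 57 − 22 − 8 = 153, which direct enumeration confirms

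No pattern falls in two rows.

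**Step 3: improvements that lose the category.** Each of the 7 CR-with-MD patterns is reached by raising one site from PR to CR. The number of such steps is 3×1 + 3×2 + 1×3 = 12, all from PR to no category.

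**Step 4: does it depend on the grid or the reading?**

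- With primary tumor and soft tissue metastasis taken as one component, there are 4^3 − 1 = 63 patterns without PD: CR 7, PR 15, MR 27, SD 10 and none 4 (3 CR with MD, 1 MD alone). The PR-to-none steps number 2×1 + 1×2 = 4.
- On the four-component grid, if MD counts as better than SD, 7 patterns of MD with SD also lose their row. If NI does not satisfy the CR row, 14 patterns of CR with NI do. The four combinations leave 8, 15, 22 or 29 patterns unclassified. The 7 CR-with-MD patterns are among them every time.

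**Step 5: scale for patients.** Each affected patient removes 1/N from the derived ORR; at the cap of 50 in section 8.1 that is 1/50 = 2.0 points. As an illustration only, assume 15 of 50 are already counted: 30% (Clopper-Pearson 95% CI 17.9% to 44.6%). Counting one more gives 16/50 = 32% (19.5% to 46.7%); three more give 18/50 = 36% (22.9% to 50.8%).

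**The case against.** The strongest reply is that a sensible programmer would close the gap. Marrow has no PR level, and the PR row ties MD to marrow and PR to soft tissue or bone, so MD can be read as the marrow counterpart of PR. On that reading no pattern is left without a category, and CR with MD is PR. This is plausible, but the row still opens by requiring a PR component and lists MD among the companions. The reading also gives the same answer as the fix, so it is an argument for writing it down.

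Other points reduce the weight:

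- BOR carries forward the best earlier visit. A patient seen at PR with MD before reaching CR with MD keeps PR, and one whose marrow later clears becomes CR. The 12 steps therefore show that the table is not ordered; they do not count patients lost.
- The order of categories stands in the BOR row and ranks assigned categories. Strictly, the table omits a case rather than stating a contrary ranking.
- A derived ORR is inferred: the repeat is stated for BOR, and ORR takes BOR as its source. The inference is reasonable.
- Section 8.7.8 says "Missing data will not be imputed with the exception of partial dates as per below". That rule concerns missing data, and assigning a category to observed components is derivation. It neither supplies a category nor forbids one. The component listings, and the promise that "the amount of missing data will be reported", may make a case visible without resolving it.
- The derived response is secondary. HCP-reported BOR and ORR, duration of response and progression-free survival do not use it, and all analyses are descriptive.

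These points limit the consequence. None of them supplies the missing rule.

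**Conclusion.** The concern holds. Followed as written, the table gives no category to CR with marrow MD when all other sites are CR or NI, nor to MD alone, while the shallower PR with MD is PR. The CR-with-MD gap appears on both grids and under every literal reading tried; it closes only if MD is treated as a marrow PR, which the text does not say.

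The size in patterns is 8 of 255 without PD (4 of 63 on the smaller grid). The size in patients is unknown: 2.0 points of derived ORR for each one at N = 50, and only for patients with no other visit classified as CR or PR. It should be corrected, but it affects a robustness check and not the main effectiveness results.

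**What to change.** 1. Extend the PR row: CR in at least one soft tissue or bone component with marrow MD, all others CR or NI and no SD or PD, is also PR. Within the table this is the only consistent category: it is not CR, and it cannot rank below PR with MD. On the four-component grid PR becomes 57 + 7 = 64 and only MD alone is left over; on the three-component grid PR becomes 15 + 3 = 18, again with only MD alone left.
2. Give MD alone its own row. The table's order does not settle the category, since SD, MR and PR all leave every pattern classified and no improvement penalized. Take it from the response criteria cited in section 8.3, and confirm item 1 against them at the same time.
3. Clarify two wordings: that the CR row means every involved component is CR and the rest NI; and whether MD with SD, without CR or PR, is SD or MR.
4. Run the derivation program over the full pattern grid. Every pattern should get exactly one category, and improving a component should never remove or worsen it.

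The cost is a few words in the table and a short program check. Data collection does not change. It is best done before the derived results are seen, so that the category is not chosen case by case.

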8.2. Setting

Clinical practice and treatment of each patient will follow as determined by each treating HCP individually. There will be no interference from Pfizer with the HCP's diagnostic and treatment decisions. The decision to treat a patient with lorlatinib will be prior to and independent of participation in the real world data collection and according to the clinical judgement of their HCP. Therefore, the data collection will in no way influence prescribing patterns or treatment decisions. If eligible, the patient will receive treatment through Pfizer's expanded access program independent of involvement in the collection of real world data.

HCPs treating a patient approved to receive lorlatinib via Pfizer's expanded access program will be invited to take part in the real world data collection. Upon HCP agreement, they will receive access to the EDC, where they can enter data into the DCT.

The first pediatric neuroblastoma patient received lorlatinib in March 2017 as part of expanded access programs and the program is ongoing. Data collection is anticipated to initiate in January 2021 and is estimated to have last patient entered into real world dataset at

PFIZER CONFIDENTIAL

the end in December 2023. Database lock would occur in February 2024, as outlined in [Section 5](#).

Data will be collected via DCT at multiple time points for patients who are receiving ongoing treatment. These timepoints will be determined by HCP standard practice for treatment and follow-up of their patients. Visits are anticipated to occur every 3-4 months, corresponding with re-supply of lorlatinib. Data will be collected on a continual basis until discontinuation of treatment with lorlatinib, death, loss to follow-up or end of study, whichever comes first.

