8.7.6 Statistical summaries

Demographic and clinical characteristics

The number and percentage of patients will be presented within each categorized variable. In addition, descriptive statistics for continuous variables will include the mean, standard deviation, median, interquartile range, minimum and maximum.

The demographics will also be presented by subgroups for any subgroups with more than 5 patients.

HCP's reported objective response

For each response component (with the exception of best response), the responses will be listed along with the date of the assessment. A derived objective response will be produced and compared to the HCP overall reported response for confirmation of robustness.

Best Overall Response (BOR) and Overall Response Rate (ORR)

For the BOR, the number and percentage of patients in each ordered category will be presented and summarized by baseline disease status. In addition, the ORR will be presented including the Clopper Pearson 95% Confidence interval.

PFIZER CONFIDENTIAL

Duration of response

The number and percentage of patients will be presented within each of the following categories for duration of response: 0 to <3 months; 3 months to <6 months; 6 months to <1 year; 1 to <2 years; 2 to <3 years >3 years; lost to follow-up. Kaplan-Meier (KM) estimates will be used to give the median, Q1 and Q3 duration of response, with 95% confidence limits. If a patient does not show symptoms of progressive disease, their duration of response will be censored at their last visit date prior to the data cut-off date.

Time to event

KM estimates will be presented, where possible, for duration of treatment, progression free survival and overall survival (i.e., time to death). The following censoring rules will be applied:

- Duration of treatment

Patients who have not discontinued treatment at the data cut-off date will be censored based on the last recorded date when the patient was known to be continuing treatment prior to the data cut-off date.

- Progression free survival

Patients who have not experienced PD or died at the data cut-off date will be censored at the date of last contact prior to the data cut-off date.

- Overall survival

[figure not shown]
Any patient not known to have died at the data cut-off date will be censored based on the last recorded date on which the patient was known to be alive prior to the data cut-off date.

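### ORR counts any single HCP-reported CR or PR with no repeat assessment, and duration of response then runs through later stable disease; a confirmed rate should be shown beside it

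*Combined protocol and SAP*

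**What the plan says.** The HCP's response call is "Collected by the DCT at each visit. Outcomes include CR, PR, minor response (MR), SD and PD" (Section 8.7.5). In the same table the BOR entry reads "Derived as the best overall response taking the HCP Reported Response observed up to the data cut-off date for a specific milestone", and the "sequence order from best to worst is CR, PR, MR, SD, PD". The ORR entry reads "Derived as Best overall response of CR+PR of the total population observed up to the data cut-off date for a specific milestone". BOR is repeated on the response derived from the tumor components.

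The DOR entry reads "Derived as (Date of PD or death, whichever occurs first) – (Date of PR or CR, whichever occurs first) + 1". Section 8.7.6 adds that, for a patient without progression, "their duration of response will be censored at their last visit date prior to the data cut-off date".

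On timing, Section 8.2 says "Visits are anticipated to occur every 3-4 months, corresponding with re-supply of lorlatinib". Collection continues until lorlatinib is stopped, the patient dies or is lost, or the study ends. Section 8.2.1 requires only one post-dose tumor assessment for inclusion. No section sets a repeat assessment, a minimum interval or a minimum duration for a CR or PR.

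**The concern.** BOR is a maximum over a patient's visits, so reading errors do not cancel. A true responder called SD at one visit is still a responder if called PR at another, whereas one mistaken or fleeting PR makes a non-responder a responder permanently. The number of calls per patient is uncapped within time on lorlatinib and differs between patients, so the opportunity for an isolated call differs too.

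The same call starts the DOR clock, and a fall back to MR or SD does not stop it.

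HCP-reported response and duration of response are named effectiveness measures (Section 7, objective 2). Section 6 foresees use of such data in regulatory submissions, and Section 11 foresees reporting to authorities and in a manuscript. Section 8.9 says responses will not be independently validated against the medical records, so persistence from visit to visit is one of the few internal checks available. With at most 50 patients (Section 8.1), each reclassified patient moves ORR by at least 1/50 = 2 percentage points.

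**Working it through.** The plan gives no assumed ORR, power or error rate, so it has no figure to reproduce. The rules can be followed on an example and the possible size illustrated.

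**1. The rules applied to one patient.** Visits are 3-4 months apart (Section 8.2). Calls are SD, PR, SD, SD, PD at visits 1 to 5.
- BOR = PR, so the patient counts in ORR.
- DOR runs from visit 2 to visit 5: 3 intervals × 3-4 months = 9-12 months (plus the one day in the formula).
- PR was recorded at one visit only and was no longer recorded 3-4 months later.
- If follow-up stops at visit 4 without PD, the patient is still a responder, with DOR censored at 2 × 3-4 = 6-8 months.

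**2. Isolated calls in a true non-responder.** Assumptions, not in the documents: probability *f* = 2%, 5% or 10% of a CR/PR call per visit, independent between visits; four visits, which at 3-4-month spacing is 12-16 months.
- At least one call: 1 − (1 − *f*)^4.
- At least two consecutive calls: 1 − (1−*f*)^4 − 4*f*(1−*f*)^3 − 3*f*²(1−*f*)² = 3*f*² − 2*f*³.

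| *f* | Any single call | Two consecutive calls |
|---|---|---|
| 2% | 1 − 0.98^4 = 7.8% | 0.1% |
| 5% | 1 − 0.95^4 = 18.5% | 0.7% |
| 10% | 1 − 0.90^4 = 34.4% | 2.8% |

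**3. Without independence.** Let *f* vary between patients as a beta distribution with mean 5% and within-patient correlation ρ, and average the same two expressions over it. For ρ = 0.1 the results are 16.2% and 1.9%; for ρ = 0.5 they are 10.1% and 4.3%. The gap narrows but keeps its direction.

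**4. What a next-visit rule removes from true responders.** Assume exponential true response duration with median *m*. The chance that response is lost before a visit *g* months later is 1 − 2^(−*g*/*m*).
- *m* = 6: 29% (*g* = 3) to 37% (*g* = 4).
- *m* = 12: 16% to 21%.

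**5. Both errors together.** Assume a true ORR of 30% and *f* = 5%, independent, over four visits.
- Unconfirmed: 0.30 + 0.70 × 0.1855 = 43.0%.
- Confirmed, if every true responder confirms: 0.30 + 0.70 × 0.0073 = 30.5%.
- Confirmed, if *m* = 6: 0.30 × (1 − 0.293) + 0.005 = 21.7%, down to 0.30 × (1 − 0.370) + 0.005 = 19.4%.

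Under these assumptions one rate lies above the true value and the other at or below it.

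**The case against.** The best case for leaving the plan alone is this. The study is descriptive, tests no hypothesis (Sections 8.5 and 8.7) and uses routine assessments. BOR is repeated on the component-derived response, dated responses are listed, and with 50 patients or fewer a reader could find an SD-PR-SD-SD sequence. Ending DOR at PD or death is a coherent definition, and the documents do not say whether SD is judged against baseline or against best response. A next-visit rule at 3-4 months tests durability as well as reading error.

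Much of this stands. No type I error or decision threshold is at stake, and step 4 shows that confirmation has its own downward bias. But the repeated BOR checks classification within a visit, not persistence, and a listing is not a summary. If SD means no change from baseline, the response is gone; if it means no change from best response, the plan should say so.

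A reader might infer more than the documents support:
- *Unlimited looks and open-ended duration.* Visits are bounded by time on lorlatinib and the milestone cut-off, and DOR without PD is censored at the last visit.
- *Three years of visits for non-responders.* The longest DOR category in Section 8.7.6 describes responders. Section 6 gives a background median OS of 16.1 months, and collection stops with treatment.
- *A bias that grows at each annual report.* An individual's BOR cannot fall, but cumulative reports also add new patients with short follow-up, and some late responses are genuine.
- *A breach of the cited INRC criteria.* Their text is not in the documents.
- *A fault in the Clopper-Pearson interval.* No binomial interval covers misclassification.

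**Conclusion.** The concern holds as an unconfirmed-response definition that the plan does not label as such. It follows from Sections 8.7.5 and 8.7.6 that one CR or PR call suffices for ORR and that later SD time counts as DOR. It also follows that isolated calls can push ORR only upward. The size does not follow from the documents: the four-visit range of 8-34% against 0.1-2.8% rests on an assumed 2-10% call rate and on independence, and a tumor assessment at every visit is itself an upper bound on the number of calls. This warrants a supportive analysis and a label. It does not warrant replacing the defined endpoints.

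**What to change.** In Sections 8.7.5 and 8.7.6:

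1. Keep ORR and DOR as defined and label both as unconfirmed.
2. Add, as supportive analyses, a confirmed ORR (CR or PR at an assessment and CR or PR again at the next one; same denominator; Clopper-Pearson interval) and DOR in confirmed responders.
3. Split the unconfirmed responders into those with no later assessment before the cut-off and those whose next assessment was below PR, the latter by MR/SD or PD. Recent responders are then not read as failures, and short responses stay visible.
4. State that, with visits 3-4 months apart, the confirmed ORR also excludes true responses shorter than the visit interval and is therefore conservative, so the two rates should be read together as a range.

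The cost is analysis programming only, since the calls and their dates are already collected (Sections 8.3 and 8.7.5). The confirmed rate can only be equal or lower. Some patients will stay unconfirmed because collection ends when lorlatinib is stopped.

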8.2.1. Inclusion criteria

Patients must meet all the following inclusion criteria to be eligible for inclusion in the study:

1. Patient treatment with lorlatinib is initiated through Pfizer's expanded access program for treatment of ALK+ neuroblastoma.
2. HCP documentation of at least one tumor assessment of response after patient has had at least one dose of lorlatinib
3. Evidence of a personally signed and dated informed consent document indicating that the patient (or a legally acceptable representative, or a waiver of informed consent has been granted by the IRB/IEC) has been informed of all pertinent aspects of the study.

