8.2.2. Exclusion criteria

Patients meeting any of the following criteria will not be included in the study:

- 1, Any patient who does not meet any of the inclusion criteria defined in the previous section.

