8.7.2 Analysis Set

Data summaries and listings will be produced on all the data collected, regardless of patients fulfilling the inclusion and exclusion criteria detailed in [Section 8.2.1](#) and [Section 8.2.2](#).

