8.7.7 Subgroups

Subgroups of interest will be explored when a sufficient amount of data are available ($n \geq 5$) Examples of subgroups that may be investigated include, but not limited, to age, disease status at baseline, and prior anti-cancer treatment. The categories associated with these subgroups are tabulated below.

PFIZER CONFIDENTIAL

Subgroup	Categories
Age	Categorized based on the distribution of age in the study population, for example: \leq 1 year; >1 to \leq 12 years; $>$ 12 years
Disease status at baseline	Recurrent/Progressive; Refractory/Resistant;
Prior anti-cancer treatment	ALK Inhibitor; Chemotherapy; Immunotherapy; Transplant; Surgery; MIBG therapy; Radiation;

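### Nothing ties the response endpoints to disease being present at lorlatinib start, so a remission already there at first dose can be counted as an HCP-reported response

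*Combined protocol and SAP*

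**What the plan says.** **Eligibility (8.2.1, 8.2.2).** There are three inclusion criteria. The first is "Patient treatment with lorlatinib is initiated through Pfizer's expanded access program for treatment of ALK+ neuroblastoma". The second is "HCP documentation of at least one tumor assessment of response after patient has had at least one dose of lorlatinib". The third is consent or a waiver. The one exclusion is "Any patient who does not meet any of the inclusion criteria defined in the previous section".

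**Analysis set (8.7.2).** "Data summaries and listings will be produced on all the data collected, regardless of patients fulfilling the inclusion and exclusion criteria detailed in" Sections 8.2.1 and 8.2.2. No response-evaluable set is defined.

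**Response endpoints (8.7.5, 8.7.6).** Best overall response (BOR) is "Derived as the best overall response taking the HCP Reported Response observed up to the data cut-off date for a specific milestone", and is then repeated with the derived response. ORR is "Derived as Best overall response of CR+PR of the total population observed up to the data cut-off date for a specific milestone", with a Clopper-Pearson 95% interval. Duration of response (DOR) runs from the first PR or CR to PD or death.

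**Derived response (8.7.5).** CR requires: "All components meet criteria for CR". A component that is not involved is provided for under PR and SD, but not under CR.

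**Baseline status.** Section 8.3 collects disease status without listing its categories. Section 8.7.6 summarizes BOR by baseline disease status. Section 8.7.7 gives, as examples, the categories "Recurrent/Progressive; Refractory/Resistant".

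**The concern.** The only disease assessment that eligibility asks for comes after the first dose. Response is a change from a starting state, and the plan does not require that state to include disease. A child brought into remission by earlier therapy who then starts lorlatinib can satisfy the criteria as written. If the HCP reports CR at the first visit, BOR takes it, ORR counts it, and the DOR clock starts at that date.

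Section 7 names HCP-reported response and duration of response as effectiveness measures. Section 11 foresees presentation to regulators and a manuscript. A reader of the ORR would take it to mean response achieved on lorlatinib, and the plan as written does not guarantee that meaning.

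**Working it through.** The plan gives no expected ORR and no power calculation (8.5), so there is no figure of its own to reproduce. The check is a reading of the rules, followed by a sizing.

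**Step 1: follow a child in remission at first dose through the rules.**

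- Eligibility: nothing in 8.2.1 or 8.2.2 excludes this child.
- Analysis set: all collected data are used, whether or not eligibility is met. Adding a disease criterion to 8.2.1 alone would therefore not change the ORR.
- HCP-reported BOR and ORR: a reported CR counts, with no condition on baseline.
- DOR: the interval opens at the date of that CR.
- Derived response: if every component is scored not involved, no row applies. The child is neither CR nor PR, but stays in the total population.

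**Step 2: inputs.**

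- N = 50, the maximum in 8.1.
- p, the response rate in children with disease: 20% to 64%, the range Section 6 reports for trials in relapsed or refractory disease. It serves only as a range for illustration and is not a lorlatinib estimate.
- f, the share in remission at first dose: not in the documents. Assumed values are 0, 10% and 20%.

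**Step 3: HCP-reported ORR, if all such children are recorded as CR.**

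ORR = f + (1 − f)p, so the inflation over p is f(1 − p).

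- f = 0: 0 points.
- f = 10%: 0.10 × 0.80 = 8.0 points at p = 20%; 0.10 × 0.36 = 3.6 points at p = 64%.
- f = 20%: 0.20 × 0.80 = 16.0 points at p = 20%; 0.20 × 0.36 = 7.2 points at p = 64%.

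In whole patients at N = 50, with Clopper-Pearson 95% intervals:

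| p | In remission at start | ORR as planned | ORR in children with disease |
|---|---|---|---|
| 20% | 5 | 14/50 = 28.0% (16.2–42.5) | 9/45 = 20.0% (9.6–34.6) |
| 20% | 10 | 18/50 = 36.0% (22.9–50.8) | 8/40 = 20.0% (9.1–35.6) |
| 64% | 5 | 34/50 = 68.0% (53.3–80.5) | 29/45 = 64.4% (48.8–78.1) |
| 64% | 10 | 36/50 = 72.0% (57.5–83.8) | 26/40 = 65.0% (48.3–79.4) |

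The last row differs by 7.0 points rather than 7.2 because responders are rounded to whole children. In the second row the planned lower limit, 22.9%, lies above the 20% rate in children with disease. With no child in remission at start, the two ORRs are identical.

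**Step 4: ORR from the derived response, if all such children fit no row.**

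ORR = (1 − f)p, which is lower than p by fp.

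- f = 10%: 2.0 points lower at p = 20%, 6.4 points lower at p = 64%.
- f = 20%: 4.0 and 12.8 points lower.

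The same children thus move the two versions of ORR in opposite directions. The gap between the versions is f(1 − p) + fp = f. At p = 20% with 5 such children it is 14/50 against 9/50, that is 28.0% against 18.0%.

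**The case against.** **The program may not admit such children.** Section 7 describes serious or life-threatening disease with standard care exhausted, inclusion speaks of treatment of the disease, and both example status categories in 8.7.7 suggest active disease. Section 8 also refers to expanded access criteria that the protocol does not reproduce. This stands as a reason why f may be zero. It is not an evaluability rule, and the analysis does not rely on it.

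**A reader might infer that the baseline split must hide these children under recurrent or progressive disease.** The documents do not support that. The 8.7.7 categories are examples, 8.7.6 does not cite them, and the categories of disease status in the data collection tool (DCT) are not shown. What can be said is that no category for absence of disease is stated.

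**A reader might infer that the derived response misses the problem, or that ORR is always biased upward.** Neither follows. A child with all components not involved would lower the derived ORR, and the planned comparison with the HCP report would show a discrepancy. Whether a component cleared before lorlatinib may be scored CR depends on response criteria (INRC) that the protocol cites but does not reproduce. The upward shift is specific to HCP-reported CR or PR. The total-population denominator does not create it; the absence of a baseline condition on who counts as a responder does.

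**The study is descriptive.** There is no hypothesis test, and 8.9 acknowledges a convenience sample. That lowers the stakes, but a descriptive ORR still needs a defined meaning.

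**Conclusion.** The gap is real: no eligibility or analysis rule requires disease at lorlatinib start, and HCP-reported BOR and ORR count any CR or PR over the total population. A remission present at first dose can be counted as a response and contribute to DOR. The documents do not determine whether that would lengthen or shorten the DOR summary.

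The inflation of HCP-reported ORR is 0 points at f = 0, 3.6 to 8.0 at f = 10% and 7.2 to 16.0 at f = 20%. This rests on two assumptions: that p lies between 20% and 64%, and that every such child is recorded as CR. The plan allows this to happen; nothing in the documents shows that it does or how often. It is worth correcting because the ORR otherwise depends on unstated coding, and the correction is cheap.

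**What to change.** 1. **DCT.** From the chart, record each component as involved, not involved or unknown at the last assessment before first dose. Record the date of that assessment and whether it precedes or follows the last prior therapy.
2. **Section 8.7.5.** Present ORR, BOR and DOR for a response-evaluable set that excludes only children documented to have no involved component at lorlatinib start. Do not exclude a child because progression was documented on prior therapy, or because no scan falls in a given window. Requiring a scan after the last prior therapy would drop children with active disease who went straight to lorlatinib, and those whose routine-care charts hold no such scan.
3. **Unknown baseline status.** Keep these children in the set, flag them, and show in a sensitivity analysis how the results change without them.
4. **Baseline disease status.** Add a separate category for children without disease at start. Keep them in PFS, OS, duration of treatment and safety.
5. **Total-population ORR.** Keep it alongside.

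The cost is a few chart-derived fields, a somewhat smaller denominator and a possibly less favourable ORR. The loss of precision is small: at a 20% response rate the interval is 10.0–33.7% for 10/50, 9.6–34.6% for 9/45 and 9.1–35.6% for 8/40. No extra procedure is needed, and neither eligibility nor treatment changes. One limit remains: a child whose last scan showed disease but who reached remission before first dose without a further scan stays in the set. The recorded order of scan and last therapy makes such cases visible.
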